**Phone:** 

### **7.1.9 Pregnancy**

Pregnancy in a registry patient must be reported to AbbVie (see contact details in Section 7.1.8) within 1 working day of the site becoming aware of the pregnancy. Information regarding a pregnancy occurrence in a registry patient and the outcome of the pregnancy will be collected. Pregnancies will be collected from the date of the patient's first dose of registry drug through 150 days following the last dose or the end of the patient's participation in the registry (whichever is longer).

Pregnancy in a registry patient is not considered an AE. However the medical outcome of an elective or spontaneous abortion, stillbirth, or congenital anomaly is considered a SAE and must be reported to AbbVie within 24 hours of the site becoming aware of the event.

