## 6.0 Investigational Plan

Patients, who agree to participate in the registry, will be followed for up to 10 years (within a registry arm), including patients who discontinue Humira (monotherapy or combination therapy with MTX) or MTX (without Humira). For patients who switch from the MTX arm to the Humira arm, the 10-year follow-up period will start at the time of enrollment into the Humira arm. This registry will assess the incidence and rate of Humira (monotherapy or combination therapy with MTX) or MTX observational and treatment-emergent SAEs, Adverse Events of Special Interest (AESI) and Pregnancy in patients diagnosed with moderately to severely active polyarticular or polyarticular-course JIA through Year 5. AESI are listed in Section 7.1.4 of this protocol. Starting at Year 6, patients will be followed annually for SAEs, a subset of AESI that includes congestive heart failure (CHF), malignancies, AEs at least possibly related to and/or leading to discontinuation of registry treatment, and pregnancies through Year 10. For polyarticular JIA patients 2 to < 4 years of age in countries with available local approval for this group

of patients at the time of consent to the registry, SAEs, all AESI, and pregnancy (at the age when a patient can become pregnant) will be collected for the full 10 years.

Patients who have discontinued or will discontinue from the registry (prior to completion of 10 years) will be contacted to determine interest in enrollment into the direct to HCP (Health Care Provider) follow-up process as described in Section 6.2. AESI, hospitalizations, surgeries and death as listed in Section 7.1.3 and Section 7.1.4 will be collected through Year 5 for those patients who choose to participate in the direct to HCP follow-up process. Starting at Year 6, patients will be followed annually for congestive heart failure, malignancies, hospitalizations, surgeries, and death through Year 10. Any other AEs, SAEs, and/or pregnancies should be reported according to normal spontaneous reporting procedures, and they are not subject to the requirements of this protocol. In countries with available local approval at the time of consent, polyarticular JIA patients 2 to < 4 years of age who discontinue for any reason, will be offered the opportunity to participate in the direct to HCP follow-up process and will be followed for AESI, hospitalizations, surgeries, and death annually for the full 10 years.

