#### **6.5 Registry Duration**

The planned follow-up observation period is 10 years from enrollment into one of the treatment arms. The follow-up period for patients that switch from the MTX arm to the Humira arm will begin when they enroll into the Humira arm, in which case participation would be longer (i.e., up to 10 years from the time of the switch).

A patient may withdraw from the registry at any time without prejudice. If the physician decides it is in the best interest of the patient to discontinue Humira or MTX for any reason, treatment should be stopped. Physicians are encouraged to keep patients in the registry for a full 10-year observation period irrespective of future treatment decisions so important and complete safety and effectiveness information can be obtained. If the patient is not seen at a visit, efforts, i.e., phone, fax, letter, will be made to gather safety data through Year 10.

Patients in the MTX arm who are prescribed Humira treatment must be re-consented before enrolling in the Humira arm during the time that the enrollment period is open (i.e., until enrollment in the Humira treatment arm is complete).

If a patient withdraws or is withdrawn from the registry, this should be noted, along with the reason for withdrawal on the electronic study completion page. At the time of withdrawal from the registry, an assessment of the patient's current medical condition will be completed.

Patients who discontinue from the registry or transition to another HCP will be offered to participate in the direct to HCP follow-up process by their registry physician, as allowed

by applicable local regulations. If the patient (or Parent/Guardian for pediatric patients) agrees, a consent/assent and/or patient authorization for use/disclosure for data (as applicable) will be obtained.

Effectiveness measures will not be collected from patients participating in the direct to HCP process.

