**Table 1. Registry Activities**

Procedure	Enrollment Visit (BL)	Month a 1 c , 3 c , 6, 12 b , 18, 24 b , 30, 36 b , 42, 48 b , 54, 60 b	Month 72, 84, 96, 108, 120	At Time of Reported Event
Informed Consent/Patient Authorization d				
Demographics, including Biological Parent Height)				
Medical/Surgical Hx (including JIA Medical/ Surgical Hx and tobacco and alcohol use)				
Pre-Registry Exposure to Humira e				
Vital Signs and Growth Assessment/ Tanner Maturation Staging b				
Safety Data Collection (AEs of Special Interest/SAEs) f				
Previous JIA therapies				
Concomitant JIA therapies				
Concomitant medications at time of reported SAE or AE of interest				
Laboratory Assessments g				
Physician Global Assessment (VAS)				
Parent's Global Assessment (VAS)				
DICHAQ				
CHQ-PF50				
Joint Assessment				
Inactive/Active Disease Status				
Eye Disease (Uveitis) Assessment				
Humira Treatment and Dosing Changes				
MTX Registry Treatment and Dosing Changes				
Case Report Form Completion				
70-Day Follow Up Call h				

- a. Data collection at regular visits that are closest to time points described. For patients participating in the HCP questionnaire process, follow-up is annually.
- b. Tanner Maturation Staging should be completed annually through Year 5, as applicable.
- c. Patients that have not rolled over from AbbVie Study DE038 or Study M10-444 will have additional visits at Month 1 and 3.
- d. Patients that switch from the MTX arm to the Humira arm must be re-consented.
- e. Medical assessments from the first dose of commercial Humira will be collected to enter into this registry.

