**Table 1. Registry Activities (Continued)**

- f. AESI, SAEs and pregnancies will be collected from Year 1 through Year 5. From Year 6 through Year 10 SAEs, a subset of AESI that includes congestive heart failure (CHF), malignancies, AEs at least possibly related to and/or leading to discontinuation of registry treatment and pregnancies will be collected. For patients that participate in the direct to HCP follow-up process AESI, hospitalizations, surgeries, and death will be collected annually from Year 1 through Year 5 and malignancies, CHF, hospitalizations, surgeries and death will be collected annually from Year 6 to Year 10. For polyarticular JIA patients from 2 to < 4 years of age while in the registry AESI, SAEs and pregnancies will be collected through Year 10 and those who participate in the direct to HCP follow-up process will have AESI, hospitalizations, surgeries and death collected annually through Year 10.
- g. Provide local lab values including but not limited to ESR, CRP, anti-nuclear antibody (ANA), and any labs related to SAE's or AEs of Special Interest (i.e., CPK, presence of lupus anticoagulants or anticardiolin antibodies). The assessments will be collected at baseline and afterwards only when part of physician's site routine care.
- h. Patients who develop an Adverse Event of Special Interest (AESI) or SAE while in the registry will be followed throughout the patient's participation in the registry or direct to HCP follow-up process until satisfactory conclusion or until 70 days following the last registry dose (whichever is longer). Follow-up received on ongoing SAEs and/or AESI post registry conclusion should be reported using standard Post Marketing Reporting.

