The procedures outlined in [Table 1](#) are discussed in detail in this section, the exception of the collection of AE information, which is discussed in [Section 7.1.1](#) and Informed consent/patient authorization which is discussed in [Section 8.0](#). For patients participating in the HCP follow-up process, follow-up is done annually as defined in the protocol and only AESI, surgeries, hospitalizations, and death are collected through completion of Year 5. Starting from Year 6 from initial registry enrollment, patients participating in the HCP questionnaire process will be followed annually for congestive heart failure, malignancies, hospitalizations, surgeries, and death through Year 10 ([Figure 1](#)). For polyarticular JIA patients 2 to < 4 years of age in countries with available local approval for this group of patients at the time of consent to the registry and participating in the HCP follow-up process will have AESI, hospitalizations, surgeries and deaths collected for the full 10 years as defined by the protocol ([Figure 2](#)). Any other AEs, SAEs, and/or pregnancies should be reported according to normal spontaneous reporting procedures, and they are not subject to the requirements of this protocol.

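### Section 7.1.9 commits to collecting pregnancies to 150 days after the last dose, but nothing scheduled delivers this for patients who leave the registry sooner than that

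*Supplement*

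**What the plan says.** Section 7.1.9 states: "Pregnancies will be collected from the date of the patient's first dose of registry drug through 150 days following the last dose". The limit in full runs "through 150 days following the last dose or the end of the patient's participation in the registry (whichever is longer". It also requires the outcome, and it makes a report due "within 1 working day of the site becoming aware of the pregnancy". Abortion, stillbirth and congenital anomaly count as SAEs there.

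Other sections describe what is done after the last dose or after leaving:

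- Table 1 lists one post-dose item, the "70-Day Follow Up Call". Its note h concerns patients who develop an AESI or SAE, who are followed "until satisfactory conclusion or until 70 days following the last registry dose (whichever is longer". Section 6.6.5 applies the same 70 days to leavers, for SAEs and AESI through Year 5 and for SAEs, CHF and malignancies in Years 6 to 10. Neither place names pregnancy.
- Section 6.5: "Patients who discontinue from the registry or transition to another HCP will be offered to participate in the direct to HCP follow-up process". Entry to that process therefore does not require that drug has stopped.
- Sections 6.6.5, 6.7.2, 7.1.7 and 7.3 describe the annual HCP questionnaire. It covers AESI (later only CHF and malignancies), hospital admissions, operations and deaths, and some of these sections add JIA medication. Pregnancy appears in none of them.
- Section 6.0 says of this process: "Any other AEs, SAEs, and/or pregnancies should be reported according to normal spontaneous reporting procedures, and they are not subject to" the protocol's requirements. Section 6.6, in the text after Table 1, repeats it: "pregnancies should be reported according to normal spontaneous reporting procedures, and they are not subject to the requirements of this protocol".

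**The concern.** The window in 7.1.9 can outlast participation, because it takes the later of two dates. For a patient who leaves on drug or soon after the last dose, the 150-day limit is the later one. The sections that govern what happens after leaving either omit pregnancy or exclude it, so a site that follows the protocol exactly would still not collect what 7.1.9 says will be collected.

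Section 6.0 names pregnancy among the outcomes whose incidence and rate the registry will assess. Pregnancy-outcome SAEs also belong to the observational safety summary. Section 10.2 counts observation time up to the last date of participation including the HCP process, and Section 10.3.1 includes HCP-process events in that summary. HCP patients thus add person-time during which abortion, stillbirth and congenital anomaly are solicited only if they surface as an admission, an operation or a death. Observational rates for these events could be understated in either arm.

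**Working it through.** The plan gives no figure to reproduce. The check compares windows.

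**Inputs.** Window after the last dose: 150 days (7.1.9). Scheduled post-dose call: day 70 (Table 1). Let d be the number of days from the last registry dose to leaving the registry.

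**Days in the 7.1.9 window with no scheduled pregnancy collection, for d < 150:**

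- Reading A, the 70-day call does ask about pregnancy: 150 − max(d, 70).
- Reading B, the call is for SAEs and AESI only, as note h is worded: 150 − d.

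| d | Reading A | Reading B |
|---|---|---|
| 0 | 150 − 70 = 80 | 150 − 0 = 150 |
| 30 | 150 − 70 = 80 | 150 − 30 = 120 |
| 70 | 150 − 70 = 80 | 150 − 70 = 80 |
| 100 | 150 − 100 = 50 | 150 − 100 = 50 |
| 150 or more | 0 | 0 |

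So the gap is 80/150 = 53% of the window for anyone leaving by day 70 under reading A. It is larger under reading B for those leaving before day 70, and it falls to zero by day 150.

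**Patients who enter HCP follow-up.** Here Sections 6.0 and 6.6 exclude pregnancy outright, so reading A is hard to sustain. How long the unmet requirement lasts turns on two undefined terms in 7.1.9:

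1. *Registry drug.* If doses taken after leaving do not count, the window closes 150 days after the last dose taken in the registry. Section 10.2 speaks of doses in the registry, which supports this reading. If they do count, a patient who stays on drug for L days after leaving has a window of L + 150 days, with pregnancy solicited on none of them.
2. *Participation.* If it includes the HCP process, as in the Section 10.2 formula for observation time, 7.1.9 requires pregnancy collection throughout HCP follow-up. Sections 6.0 and 6.6 disclaim exactly that. If it excludes the HCP process, the 150-day tail is still not delivered for early leavers.

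Neither meaning of participation makes the text consistent. Section 7.3 records Humira and MTX start and stop dates each year during HCP follow-up, so the protocol foresees exposure in that phase.

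**Patients who stop drug but stay.** Sections 6.6 and 6.8.1 encourage them to remain, with visits or maintained contact. Section 6.6.5 collects pregnancies at any time, and Section 6.8.1 names them in Years 6 to 10. Once such a patient has stayed 150 days past the last dose, the 150-day limit is met.

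**The case against.** The strongest counter-argument is that the HCP process is deliberately simplified and its pregnancy exclusion is stated twice. On that view only 7.1.9 needs rewording and a new questionnaire item is an enhancement. This has some force, since aligning the wording is the essential correction. But 7.1.9 is unqualified and 6.0 makes pregnancy an assessed outcome, so the conflict has to be settled one way or the other.

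Four stronger readings are tempting, and the documents do not support them.

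- *The 70-day call is the only contact after the last dose.* This is not so for patients who stop drug and remain.
- *Every leaver has 80 uncovered days.* The figure holds only for leaving by day 70, with the call read as covering pregnancy. The gap shrinks after that.
- *These pregnancies and SAEs are lost.* Section 7.1.9 still requires a report once a site is aware, spontaneous reporting continues, Section 6.7.2 speaks of SAE reporting during the HCP process, and the questionnaire's admission, operation and death items would catch some outcomes. An outcome SAE within 70 days may also fall under the SAE follow-up.
- *The affected group can be counted.* One might take the 68% dropout in Section 10.6 (0.68 × 500 = 340) and the 2.5:1 sex ratio in Section 3.0 (2.5/3.5 = 71%, about 240 girls). But the 68% is an allowance that reduces Humira exposure from 2500 to about 1500 patient-years. It does not say who leaves the registry or how soon after a dose. The ratio describes JIA in general, and no share of childbearing age is given.

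It is also fair that a late contact cannot reach patients who withdraw consent or are lost to follow-up, and that HCP follow-up needs its own consent and local permission. Section 10 specifies no pregnancy summary, and the sample size is untouched.

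**Conclusion.** The point holds for patients who leave the registry less than 150 days after the last dose, including those who move to another provider while on drug. For them the protocol states a collection window that its own procedures do not deliver. In days, the shortfall is 80 of 150 when leaving by day 70 if the 70-day call covers pregnancy, up to 150 if it does not, and zero from day 150 on. In patients, it cannot be sized from the documents. The consequence is that such pregnancies and their outcomes are not actively solicited while HCP time still counts as observation time.

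This rests on the text. Figures 1 and 2, the cell marks of Table 1 and the questionnaire itself are not visible in the documents reviewed, so the absence of a pregnancy item is inferred from how the questionnaire is described.

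**What to change.** 1. Reconcile Section 7.1.9 with Sections 6.0, 6.6 (including Table 1 note h), 6.6.5 and 7.3.
2. State in 7.1.9 whether participation includes the HCP process, as it does in Section 10.2, and whether doses taken after leaving count as registry drug.
3. To deliver the 7.1.9 commitment, add pregnancy occurrence and outcome to the existing annual HCP questionnaire for all years, and take pregnancies out of the sentence in Sections 6.0 and 6.6 that leaves them to spontaneous reporting.
4. For leavers who still consent and can be reached, make one data-collection contact at the end of the 150-day window.

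The cost is one questionnaire item and a small amount of site contact by phone or letter. It changes data collection only. Patients who withdraw consent or are lost to follow-up stay uncovered, and the report should say so.

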## **7.2 Product Complaint**

### **7.2.1 Definition**

A Product Complaint is any Complaint (see Section 7.0 for the definition) related to the biologic or drug component of the product or to the medical device component.

For a product this may include, but is not limited to, damaged/broken product or packaging, product appearance whose color/markings do not match the labeling, labeling discrepancies/inadequacies in the labeling/instructions (example: printing illegible), missing components/product, device not working properly, or packaging issues.

For medical devices, a product complaint also includes all deaths of a patient using the device, any illness, injury, or adverse event in the proximity of the device, an adverse event that could be a result of using the device, any event needing medical or surgical intervention including hospitalization while using the device and use errors.

Any information available to help in the determination of causality by the device to the events outlined directly above should be captured.

### **7.2.2 Reporting**

Product Complaints concerning the product and/or device must be reported to the Sponsor within 24 hours of the study site's knowledge of the event via local Product Complaint reporting practices. Product Complaints occurring during the study will be followed-up to a satisfactory conclusion. All follow-up information is to be reported to the Sponsor (or an authorized representative) and documented in source as required by the Sponsor. Product Complaints associated with adverse events will be reported in the study summary. All other complaints will be monitored on an ongoing basis.

Product Complaints may require return of the product with the alleged complaint condition (syringe, pen, etc.). In instances where a return is requested, every effort should be made by the investigator to return the product within 30 days. If returns cannot be accommodated within 30 days, the site will need to provide justification and an estimated date of return.

The description of the complaint is important for AbbVie in order to enable AbbVie to investigate and determine if any corrective actions are required.

Product complaints involving a non-Sponsor drug, device or combination product, under study, should be reported to the identified contact or appropriate manufacturer, as necessary per local regulations.

### **7.3 Data Collection Procedures for Patients Who Participate in the Direct to HCP Process**

For patients participating in the direct to HCP process, HCPs will document any Adverse Event of Special Interest, hospitalizations, surgeries, and death as defined in Section 7.1.3 annually via a paper questionnaire or eCRF through the first 5 years of the patient's enrollment date in the registry. HCPs will document any occurrence of hospitalizations, surgeries, death, malignancies, and CHF annually via a questionnaire or eCRF beginning at Year 6 through Year 10. HCPs will document any occurrence of a subset of AESI that includes congestive heart failure and malignancies, hospitalizations, surgeries, and death

annually via a questionnaire or eCRF beginning at Year 6 through Year 10. For polyarticular JIA patients 2 to < 4 years of age in countries with available local approval for this group of patients at the time of consent to the registry the AESI, hospitalizations, surgeries and death will be collected for the full 10 years as defined by the protocol (Figure 2). The HCP will collect and record the date of onset (where known), and description of the event. The use of other medications used to treat polyarticular JIA, and the start and stop dates for Humira and/or MTX will be collected on an annual basis.

Effectiveness data will not be collected as part of the direct to HCP process.

## **8.0 Ethics and Quality**

The applicable informed consent/patient assent form or patient authorization will be obtained from the parent or legal guardian at the Baseline visit before any registry procedures are undertaken. Additionally, a written informed assent must be obtained from all children 9 years old or according to the local regulations prior to any registry-related procedures. If a patient becomes of legal age during the course of the registry, that patient will need to be re-consented.

Prior to consenting, the Physician or designee will explain to the parent or legal guardian and to the patient the nature and purpose of the registry and the data to be provided to the sponsor. Upon consent, the parent or legal guardian is allowing the release of patient's information to AbbVie (Sponsor), which can be modified according to local requirements. After the informed consent/patient authorization form is signed, the form will be placed in the patient's medical record and a signed copy should be given to the patient.

Patients that prematurely discontinue from the MTX arm of this registry and meet the requirements for entry in the Humira arm will need to re-consent.

### **8.1 Quality Assurance**

Every registry site will obtain IEC/IRB approval, if applicable (of this registry protocol and related informed consent/patient authorization), prior to initiating the registry at that

site. It shall be the Physician's responsibility to secure such approval prior to further initiating any registry procedures.

The Investigator or his/her representative will explain the nature of the registry to the patient's parent or legal guardian, and answer all questions regarding this registry. Prior to any registry-related screening procedures being performed on the patient, the informed consent/patient authorization form will be reviewed and signed and dated by the patient's parent or legal guardian and the person who administered the informed consent/patient authorization form. Additionally, a written informed assent must be obtained from all children 9 years old prior to any registry-related procedures or according to age restrictions of the local regulations. If a patient becomes of legal age during the course of the registry, that patient will need to be re-consented.

A copy of the informed consent/patient authorization and informed assent form(s) will be given to the patient and the original will be placed in the patient's medical record. An entry must also be made in the patient's dated source documents to confirm that informed consent/patient authorization was obtained prior to any registry-related procedures and that the patient received a signed and dated copy. A copy of the patient signed informed consent/assent or patient authorization form (as applicable) will be provided to the HCP.

Prior to the site's initiation of the registry, a Physician's meeting will be held with AbbVie personnel, the physicians, and their coordinators, the UBC project manager and the CRAs for the registry. This meeting will include a detailed discussion of the protocol, performance of registry procedures and paper and eCRF completion. In addition to or instead of the Physician's meeting, the personnel at each site may be trained on the registry procedures via web-based training, by a CRA at a registry initiation visit via the telephone or on site and will be given a paper and eCRF completion workbook for reference.

At least one monitoring visit will be performed at each site for the duration of the registry. During the monitoring visit entries on the eCRF are reviewed against source documents to verify accuracy and appropriate completion of the eCRF. The monitoring plan will detail

how sites will be selected for the monitoring visits and what data will be source data verified during the visit. Throughout the registry, UBC and AbbVie (if needed) will periodically follow-up with the sites to ensure that SAEs and Adverse Events of Special Interest are being reported.

All data will be entered in the registry via the eCRF and questionnaires will be completed on paper CRFs. All eCRF information will be imported directly into the electronic data capture system. Paper case report forms are first quality controlled checked and then entered into the electronic data capture system. All other paper questionnaires (e.g., direct to HCP questionnaire) will be reviewed for completion by the site or the CRO (as appropriate) prior to being entered into the database. After entry of the data, computer logic checks will be run to check for inconsistent registry data. Any necessary corrections will be made to the database and documented via addenda, queries, supplemental data clarification form (SDCF) or audit trail. A manual review of selected line listings will also be performed at the end of the registry.

The Investigator should not implement any deviation from the protocol without prior review and agreement by the Sponsor **and** in accordance with the IEC/IRB and local regulations, except when necessary to eliminate an immediate hazard to registry patients. When a deviation from the protocol is deemed necessary for an individual patient, the Investigator must contact their monitor upfront who will contact the Sponsor.

Such contact must be made as soon as possible to permit a review by AbbVie to determine the impact of the deviation on the patient and/or the registry. Any significant protocol deviations affecting patient eligibility and/or safety must be reviewed and/or approved by the IEC/IRB and regulatory authorities, as applicable, prior to implementation.

